9.3.1. Progression Free Survival (PFS) per BIRC between Single-Agent Cabozantinib and Control Arms

The analysis of PFS as a secondary endpoint is event-driven and will be conducted after at least 283 events have been observed in the ITT population (see [Section 9.1.1](#)) for the single-agent cabozantinib and control arms. It is designed to include progression events as determined by the BIRC per RECIST 1.1. General censoring rules as described in [Section 9.2.2.1](#) will be applied.

Hypothesis testing between the two treatment arms will be performed using the stratified log-rank test at the 2-sided α level (the α level will be defined per [Section 9.5](#)) in the ITT population, provided the null hypothesis for either PFS or OS is rejected in favor of the experimental arm (cabozantinib + atezolizumab) as described in [Section 9.5](#). The stratification factors will be the same as those used to stratify the randomization (see [Section 3.3](#)).

The median duration of PFS and the associated 95% and 99% CIs for each treatment arm will be estimated using the Kaplan-Meier method. The HR with 95% and 99% CIs will be estimated using a Cox regression model and will include the same stratification factors described above.

In the secondary analysis of PFS, if the p-value for the stratified log-rank test is statistically significant and the HR ($\lambda_{\text{cabozantinib}} / \lambda_{\text{sorafenib}}$) is < 1 , the null hypothesis of no difference between the two treatment arms in PFS will be rejected and it will be inferred that PFS is superior in the group receiving single-agent cabozantinib compared with the group receiving sorafenib.

One interim analysis of secondary PFS is planned at approximately 67% information fraction. Details are provided in [Section 9.8](#).

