9.5. Control of Type I Error

Inflation of Type 1 error associated with testing of multiple primary endpoints and a secondary efficacy endpoint (PFS between single-agent cabozantinib and control) will be controlled by a modified Bonferroni procedure, a gatekeeping technique, and the fallback method (FDA 2017). Initially, the study-wise 2-sided alpha of 5% will be unequally allocated between primary endpoints PFS (1%) and OS (4%). The secondary PFS endpoint will be tested at the 1% level only if the primary PFS test is successful. If the null hypotheses are rejected for both the primary and secondary PFS endpoints, the 1% alpha for PFS will be reallocated to OS, allowing it to be tested at the 5% level.

Two interim analyses of OS are planned at the 33% and 66% information fractions (the first interim will coincide with the primary analysis of PFS and will be performed only if the null hypothesis for PFS is rejected and is expected to occur at approximately the 33% information fraction). One interim analysis is planned for secondary PFS endpoint contemporaneous with the primary PFS analysis with anticipated information fraction of 67%. Type 1 error associated with interim analyses will be controlled using Lan-DeMets O'Brien-Fleming (LD-OF) alpha-spending functions based upon a 4% total alpha allocation for OS and 1% for secondary PFS.

The testing and alpha reallocation are elucidated below.

First, test primary PFS at the 1% level. Then:

1. If primary PFS is significant:
 - a. Re-allocate its 1% alpha to secondary PFS per the fallback method.
 - b. Conduct interim analysis of OS at 33% per LD-OF with 4% total alpha
 - c. Conduct interim analysis of secondary PFS endpoint at 67% per LD-OF with 1% alpha.
 - i. If interim analysis of secondary PFS is significant:
 - Re-allocate its 1% alpha to OS
 - Conduct interim analysis of OS at 66% per LD-OF with 5% alpha
 - No further inferential testing of secondary PFS will be performed.

- ii. If interim analysis of secondary PFS is not significant:
 - The final analysis of secondary PFS will be conducted at an alpha of 0.0096.
 - The alpha of subsequent OS analyses will be dependent on the timing and result of the final secondary PFS analysis.

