For OS, a total of 368 deaths among all 555 subjects randomized in a 2:1 ratio in the experimental (n=370) and control arms (n=185) are required to provide 90% power to detect an HR of 0.69 using the log-rank test and a 2-sided significance level of 4%. Assuming an exponential distribution for OS, this corresponds to a 45% increase in median survival from 12.3 months to 17.8 months. The minimum observed effect that would result in statistical significance for the primary analysis of OS is an HR of 0.7942, a 26% improvement in median from 12.3 to 15.5 months.

For the secondary endpoint of PFS for the single-agent cabozantinib arm vs the control arm (sorafenib), a total of 283 events among all 370 subjects (185 per arm) in the single-agent cabozantinib and control arms provides the study with 85% power for a 2-sided log-rank test with a 1% level of significance to detect a hypothesized true HR of 0.65. Assuming an exponential distribution for PFS, this corresponds with a 53% increase in median PFS from 3.6 months to 5.5 months. The minimum observed effect that would result in statistical significance for PFS is an HR of 0.735, a 36% improvement in median from 3.6 to 4.9 months.

With an average accrual rate of 30 subjects per month it is estimated that it will take approximately 18.4 months to observe the required primary PFS events (16.5 months of subject accrual) and approximately 38 months to observe the required deaths for OS (25 months of subject accrual) to evaluate the primary endpoints in the combination and control arms.

Assuming the same accrual rate, it is anticipated that it will take approximately 25 months to

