^d The interim analysis at 66% information fraction will be conducted at 4% alpha level if it occurs prior to the secondary PFS analysis. It will be conducted at 4.96% alpha level if it happens after the null hypothesis for secondary PFS is rejected at the time of final analysis. It will be conducted at 5% alpha level only if the null hypothesis for secondary PFS is rejected at the interim analysis.

Rejection of the null hypotheses for OS at the first interim analysis at about 33% information is not expected: it is designed primarily as an administrative analysis, expected to coincide with the primary analysis of PFS, and will be performed only if the null hypothesis for PFS is rejected.

Should the timing of the first interim analysis (IA1) of OS trend towards an information fraction much higher than expected (eg, due to faster-than-expected deaths or slower-than-expected PFS events), the interim analyses of OS will be conducted as follows:

OS IA1 IF	Proceed as	Rationale
< 50%	perform IA1 and IA2 as planned above	similar conditions to original plan
50 to < 66%	
 perform IA1 at time of primary PFS, irrespective of whether PFS null hypothesis is rejected or not Conduct IA2 at 80% IF (instead of 66%) 	
 Higher than expected information for OS negates administrative nature of the analysis. Preserves two interim analyses as planned with reasonable intervals between them
≥ 66%	perform a single interim analysis at 66% IF, irrespective of timing or results of primary PFS analysis.	Information fraction meets or exceeds that of planned analysis at 66%

IA1, first interim analysis; IA2, second interim analysis; IF, information fraction; OS, overall survival

An interim analysis of secondary PFS is planned contemporaneously with the primary PFS analysis and will be conducted only if the null hypothesis for primary PFS is rejected. It is anticipated to be at approximately 67% information fraction based on a total alpha of 1%. At this fraction, the critical p-value is 0.0096, and the maximum HR to reject the null hypothesis is 0.626.

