Due to logistical considerations in event ascertainment and operational planning and conduct, the actual analyses may include more or fewer events than the target information fractions. The actual critical values employed at the interim and final analyses of secondary PFS and OS will depend upon the actual information fraction at the time of the analyses. Descriptive supportive analyses will be provided at the planned information fraction at the time of the analyses.

If a null hypothesis is rejected for a given endpoint at interim analysis (secondary PFS or OS), no subsequent testing of that endpoint will be performed.

Interim analysis of primary PFS and futility analyses of PFS or OS are not planned.

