For OS, a total of 368 deaths among all 555 subjects randomized in a 2:1 ratio in the experimental (n=370) and control arms (n=185) are required to provide 90% power to detect an HR of 0.69 using the log-rank test and a 2-sided significance level of 4%. Assuming an exponential distribution for OS, this corresponds to a 45% increase in median survival from 12.3 months to 17.8 months. The minimum observed effect that would result in statistical significance for the primary analysis of OS is an HR of 0.7942, a 26% improvement in median from 12.3 to 15.5 months.

For the secondary endpoint of PFS, a total of 283 events among all 370 subjects (185 per arm) in the single-agent cabozantinib and control arms provides the study with 85% power for a 2-sided log-rank test with a 1% level of significance to detect a hypothesized true HR of 0.65. Assuming an exponential distribution for PFS, this corresponds with a 53% increase in median PFS from 3.6 months to 5.5 months. The minimum observed effect that would result in statistical significance for PFS is an HR of 0.736, a 36% improvement in median from 3.6 to 4.9 months.

With an average accrual rate of 30 subjects per month it is estimated that it will take approximately 18.4 months to observe the required primary PFS events (16.5 months of subject accrual) and approximately 38 months to observe the required deaths for OS (25 months of subject accrual) to evaluate the primary endpoints in the combination and control arms. Assuming the same accrual rate, it is anticipated that it will take approximately 25 months to observe the required secondary PFS events (25 months of subject accrual) to evaluate the secondary endpoint in the single-agent cabozantinib and control arms. These estimates are based upon the statistical assumptions, adjusted to accommodate the time required for all study sites to be activated and for subject recruitment to reach full potential. The true intervals required to meet these milestones may be longer or shorter due to divergence from assumptions, including non-constant accrual rate due to the time required for all study sites to become active. The sample size was increased to up to 837 subjects to ensure the needed enrollment of at least 185 subjects in the single-agent cabozantinib arm.

An overview of the endpoints and operating characteristics is shown in Table 3:

Table 3: Summary of Endpoint Operating Characteristics

Accrual per month	30 subjects		

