7.2 Control of Type I Error

Inflation of Type 1 error associated with testing of multiple-primary endpoints and a secondary efficacy endpoint (PFS between single-agent cabozantinib and control) will be controlled by a modified Bonferroni procedure and a parallel gatekeeping method (FDA 2017). Initially, the study-wise 2-sided alpha of 5% will be unequally allocated between primary endpoints PFS (1%) and OS (4%). The secondary PFS endpoint will be tested at the 1% level only if the primary PFS test is successful. If the null hypotheses are rejected for both the primary and secondary PFS endpoints, the 1% alpha for PFS will be reallocated to OS, allowing it to be tested at the 5% level.

Two interim analyses of OS are planned at the 33% and 66% information fractions (the first interim will coincide with the primary analysis of PFS and will be performed only if the null hypothesis for PFS is rejected analysis and is expected to occur at approximately the 33% information fraction). Type 1 error associated with interim analyses will be controlled using Lan-DeMets O'Brien-Fleming (LD-OF) alpha-spending functions based upon a 4% total alpha allocation for OS. However, if the null hypotheses are rejected for both the primary and secondary PFS endpoints, the 1% alpha for PFS will be reallocated to OS per the fallback method. As a consequence, the final OS analysis will employ critical values from the spending function at 5% level. The alpha level of the interim analysis at 66% will be dependent on the timing of the interim analysis. It can be conducted at 5% alpha level only if it occurs after the null hypothesis for the secondary PFS is rejected. (see Section 7.3).

All other statistical evaluations of efficacy will be considered exploratory.

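### Protocol 9.8 prints the final-look critical p-value (0.0096) as the secondary-PFS interim boundary; the plan's own spending rule gives about 0.0012

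*Protocol*

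**What the plan says.** **Protocol.** Section 9.5 controls the interim looks with LD-OF "alpha-spending functions based upon a 4% total alpha allocation for OS and 1% for secondary PFS", and its stepwise scheme applies this to the secondary-PFS interim at 67% information. If that interim fails, "The final analysis of secondary PFS will be conducted at an alpha of 0.0096". Section 9.8 then gives the interim boundary: "At this fraction, the critical p-value is 0.0096, and the maximum HR to reject the null hypothesis is 0.626". It adds: "The actual critical values employed at the interim and final analyses of secondary PFS and OS will depend upon the actual information fraction". Section 9.7 plans 283 events with 1:1 allocation, a two-sided 1% level, 85% power at HR 0.65, and gives the final threshold: "The minimum observed effect that would result in statistical significance for PFS is an HR of 0.735". The decision rule in Section 9.3.1 rests on the p-value: "In the secondary analysis of PFS, if the p-value for the stratified log-rank test is statistically significant and the HR" is below 1, the null hypothesis is rejected. That section takes its alpha level from Section 9.5.

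**SAP.** Section 7.2 describes "alpha-spending functions based upon a 4% total alpha allocation for OS" and does not extend the spending function to secondary PFS. Section 7.3 gives 67% information and 1% total alpha for the secondary-PFS interim, with no function and no boundary. Its sentence on recalculating critical values names OS only. Section 7.4.1 refers for method to Section 7.1.1.6, where the test level is a flat two-sided 0.01. The addendum ties alpha-spending to the events available at the analysis, again without naming a function. Section 2.3 says: "The minimum observed effect that would result in statistical significance for PFS is an HR of 0.736".

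**The concern.** The same value, 0.0096, appears as the critical p at the interim (9.8) and at the final analysis (9.5). Under O'Brien-Fleming-type spending the boundary at 67% information must be much stricter than at the end, so both cannot be right. The HR printed beside the interim p is already that much stricter boundary.

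Secondary PFS is inside the alpha-controlled hierarchy. A rejection at its interim ends testing of that endpoint and releases 1% alpha to OS, a primary endpoint. A result between the two readings would leave two prespecified answers, to be settled after the data had been seen.

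**Working it through.** **Inputs.** Two-sided alpha 0.01 and LD-OF (Protocol 9.5); 283 events, 1:1 allocation, HR 0.65 (9.7); interim at about 67% (9.8), taken as 190 events, so t = 190/283 = 0.671.

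**1. The design reproduces.** The Schoenfeld formula for HR 0.65, alpha 0.01, power 85% and 1:1 allocation gives 282 events. Fixed-design power at 283 events is 85.3%, against the stated 85%.

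**2. The convention reproduces the OS table.** With symmetric two-sided LD-OF at looks 1/3, 2/3 and 1, the OS critical p-values at 4% alpha are 0.00011, 0.00873 and 0.03726 (printed: 0.00011, 0.00867, 0.03728). At 5% they are 0.00021, 0.01202 and 0.04626, exactly as in SAP Table 11.

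**3. Secondary-PFS boundaries under the same convention.** Cumulative spend per tail is 2·[1 − Φ(z(0.9975)/√t)]. The final bound comes from the bivariate normal distribution with correlation √t. The HR bound is exp(−2z/√D), where D is the number of events.

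| Look | Events | z | Two-sided p | HR bound | Protocol prints |
|---|---|---|---|---|---|
| Interim | 190 | 3.2328 | 0.00123 | 0.6256 | p 0.0096, HR 0.626 |
| Final | 283 | 2.5899 | 0.00960 | 0.7350 | p 0.0096, HR 0.735 |

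The exact fraction does not matter: the interim p is 0.00110 at t = 0.66, 0.00117 at 2/3 and 0.00121 at 0.67. Applying LD-OF directly to the two-sided 0.01 gives 0.0015 to 0.0017 at the interim and 0.0094 at the end, which matches neither printed figure.

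**4. The printed pair is inconsistent within itself.**
- HR 0.626 at 190 events: z = 0.4684 × √190/2 = 3.228, p = 0.00125.
- p = 0.0096 at 190 events: HR = exp(−2 × 2.5899/√190) = 0.687.
- p = 0.0096 at 283 events: HR = exp(−2 × 2.5899/√283) = 0.735, the final threshold in 9.7.

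Section 9.5 also allots OS 4.96% after a rejection at the final secondary-PFS analysis, that is 4% + 0.96%. This again places 0.0096 at the final look.

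**5. Effect of using 0.0096 at both looks, once primary PFS has been rejected.**
- Two-sided type I error: 1.57% instead of 1.00% (1.63% with the interim at 60% information, 1.50% at 75%).
- False superiority over both looks: 0.79% instead of 0.50%.
- False superiority at the interim alone: 0.0096/2 = 0.48% instead of 0.00123/2 = 0.06%.
- Interim rejection at a true HR of 0.65: mean of Z = 0.4308 × √190/2 = 2.969. This gives Φ(2.969 − 2.590) = 64.8% with the printed p and Φ(2.969 − 3.233) = 39.6% with LD-OF. The difference, about 25%, is the chance of an observed HR between 0.626 and 0.687.

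**6. The SAP's 0.736.** A fixed test at p = 0.01 with 283 events gives exp(−2 × 2.5758/√283) = 0.7362. The SAP figure therefore ignores the interim look.

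**The case against.** The strongest reply is that the Protocol's governing rule is right. Section 9.3.1 sends the reader to 9.5 for the alpha level. Section 9.5 and the synopsis both specify LD-OF with 1% total alpha. Section 9.8 itself says the critical values will be recalculated at the actual information fraction. On this view the 0.0096 in 9.8 is a transcription slip in an illustration, exposed by the correct HR next to it, and the inflation arises only if the analyst departs from the rule. The SAP never repeats the wrong number, and its 0.736 agrees with its own wording about a 1% level.

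Most of this stands as a limit on the practical risk: followed as written, 9.5 causes no inflation. It does not rescue the printed value. Recalculation covers departures from the target fraction, whereas 0.0096 is wrong at the target fraction itself. Section 9.5 gives the rule but no interim number, so 9.8 is the only place where a reader finds one. The SAP offers no correction: Section 4.9 says that a typographical error in the Protocol is put right in Table 11, but that table covers OS only. The 0.736 is indeed minor, a third-decimal planning figure with no decision attached.

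**Conclusion.** The concern holds. Protocol 9.8 pairs the correct interim HR (0.626) with the final-look p-value. The interim critical p should be about 0.0012, so the printed threshold is about eight times too large (0.0096/0.0012 = 8).

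The error inflation (1.57% against 1.00%) is conditional: primary PFS has been rejected, and 0.0096 is applied at both looks. The calculation assumes 283 total events, 1:1 allocation and 190 events at the interim. The p-value boundary depends on the information fraction and not on the allocation. A wrong decision threshold for a confirmatory test that feeds alpha to OS must be corrected before the interim is run.

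**What to change.** - **Protocol 9.8:** replace 0.0096 with about 0.0012, keep HR 0.626, and give 0.0096 with HR 0.735 as the final boundary.
- **SAP 7.2 and 7.3:** state that LD-OF spending with 1% total two-sided alpha, recomputed at the actual information fraction, applies to secondary PFS. Add its interim (0.0012 / 0.626) and final (0.0096 / 0.735) boundaries.
- **SAP 2.3:** change 0.736 to 0.735 to match Protocol 9.7.

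The cost is one number and one label in the Protocol, and one sentence, two boundary rows and one digit in the SAP. Events and patients do not change. Power at HR 0.65 with the correct boundaries is 85.1%, in line with the stated 85%.

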9.9. Analysis Methodology for China Subpopulation

The primary scope of the China subpopulation analysis is to allow evaluation of consistency in efficacy and safety with the global study population per NMPA guidance. Since the China subpopulation is not powered to demonstrate statistical significance in terms of efficacy, no formal hypothesis testing will be performed. All data summaries for the China subpopulation (to include all subjects from China from the global and Mainland China Extension phases) will be descriptive. The safety and efficacy data in the China subpopulation will be analyzed separately for the same endpoints using the same analysis methods as for the global population. The analyses for this subpopulation will be performed when the data are of sufficient maturity to allow evaluation of consistency in efficacy and safety.

Details of the planned summaries will be provided in a separate SAP for the China subpopulation that will be finalized before the last subject is randomized in the China.

10. OTHER ANALYSES

10.1. Pharmacokinetic Analyses

The plasma concentration of cabozantinib will be analyzed by the designated laboratory using a validated bioanalytical method. Descriptive statistics (eg, number, mean and/or median, standard deviation, and coefficient of variation) will be used to summarize the concentration-time data per visit. Where appropriate, these data may be combined with data from other studies as part of a meta-analysis (ie, population PK analysis). The effect of cabozantinib exposure on biomarkers, clinical safety parameters (eg, selected AEs), or clinical response may also be explored.

Serum concentrations of atezolizumab will also be measured and summarized. Descriptive statistics (eg, number, mean and/or median, standard deviation, and coefficient of variation) will be used to summarize the concentration-time data per visit.

10.2. Immunogenicity Analyses

Results of anti-drug antibody (ADA) testing (ie, immunogenicity testing) will be summarized overall as the number of subjects with ADA at any time point. The association between human ADA incidence, PK, and efficacy and/or safety outcomes may be explored.

10.3. Biomarker Analyses

Analyses may include MET and PD-L1 expression and other analyses (eg, tumor mutational burden) with clinical response.

11. DATA QUALITY ASSURANCE

Accurate and reliable data collection will be assured by verification and cross-check of the CRFs against the Investigator's records by the study monitor (source document verification) and by the maintenance of a drug-dispensing log by the investigator. Authorized study site personnel will enter data directly into a computerized CRF database (ie, electronic data capture [EDC] system). Study databases will be subject to electronic and manual quality assurance procedures.

12. STUDY COMMITTEES

12.1. Executive Safety Committee (ESC)

The Sponsor's Executive Safety Committee (ESC) provides safety oversight over periodic and ongoing reviews on product safety data and blinded study data (through a Safety Management Team). The ESC provides the company position and actions for all safety aspects of the company's product to protect patient safety and public health. The ESC is managed and chaired by the Head of Drug Safety, and includes the following other members: Chief Medical Officer, Head of Clinical Development, Head of Regulatory Affairs and qualified representatives of other functional groups as appropriate.

